## Statistical analysis plan for KetMo, NCT 05422001

Aarhus. September 15th 2023

The following plan for data analysis was decided upon at a meeting with all members of the steering committee on September 15th, 2023. The plan was made before A and B lists were obtained from the hospital pharmacy.

This study will be undertaken as an equivalence trial with the application of intention to treat analysis.

Missing data are assumed to be missing at random, no imputations.

In brief:

A study enrollment flow diagram in accordance with the CONSORT (Consolidated Standards of Reporting Trials) will be prepared. Patient characteristics and outcome measures will be reported as means, standard deviations (SDs), medians, interquartile ranges (IQRs), and percentages, as appropriate.

Primary outcome will be comparing average change of NRS at 10 minutes between the intervention and control group and analyzed using appropriate test depending on distribution. Primary outcome includes initial analysis of all included patients (n=116) and sub-analysis in two groups (prior opioid use / no prior opioid use). Appropriate test according to potential difference in NRS at T0 in the two groups (prior opioid use) will be applied for comparing the differences in NRS between the two groups.

NRS will be reported as median (interquartile range) and compared between groups at the various times using the Mann–Whitney U test. If normal distributed a multilevel mixed effects linear regression will be carried out.

Categorical data (number of patients with Ramsay Sedation Scale Level 2, any adverse events during observation) are reported as numbers (%) with 95% confidence intervals and compared using the  $\chi^2$  test. Analysis of other secondary outcomes will be dichotomized and presented for relevant time points,  $\chi^2$  test.

Secondary outcome concerning Rescue opioid will be evaluated as time to event (opioid) – non parametric – Kaplan Meier estimate will be considered, if appropriate. Alternative rescue opioid yes/no – binary regression if assumptions are fulfilled.

All P-values will be two-sided, and those below 0.05 considered significant.

Detailed statistical plan are written, printed, signed and stored in Trial Master File

[name]

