## 2. TRIAL DESIGN, OBJECTIVES AND HYPOTHESES

#### 2.1 Overview

#### 2.1.1 Design

This is an investigator-initiated, randomized, parallel-grouped, double-blinded, superiority trial, investigating the combination of IV LDK and IV morphine versus IV morphine and placebo as regards to analgesic effect.

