## 2.1.2 Hypotheses

- The combination of IV LDK and IV morphine will be superior to IV morphine alone as regards analgesic effect measured as reduction on the NRS scale.
- The combination of IV LDK and IV morphine will provide a larger reduction on the NRS scale for patients with a prior use of opioids than for patients with no prior use of opioids.
- The combination of IV LDK and IV morphine will reduce the opioid consumption within the first hour.
- The frequency of side effects will be similar in the two treatment groups (ketamine vs. placebo)

\*\* After longer use (> 3 days).

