#### 4.1.2 Rationale

This study is powered to detect a difference in pain reduction of at least 1.5 on the NRS scale between the groups. (LDK vs placebo)

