#### 5. SAMPLE SIZE CALCULATION AND STATISTICAL ANALYSIS PLAN

## 5.1 Sample size calculation

We consider a mean reduction in pain intensity of 1 (SD  $\pm$ 2) on the NRS scale to be realistic in the control group and that the reduction should be 2.5 (SD  $\pm$  2) in the intervention group for the addition of LDK to be meaningful. Based on these estimates, an alpha of 5%, a power of 90% and a two-sample t-test (assuming that the pain reduction is normally distributed), a sample size of 78 patients is required; 39 in each treatment arm (two independent samples =156 patients).

The primary (continuous) and secondary outcomes (binary and continuous variables) will be presented as follows: Categorical variables will be compared using Fisher's exact test and continuous variables

using t-tests or Wilcoxon rank-sum test as appropriate. P < 0.05 will be considered statistically significant.

To investigate the hypothesis of heterogeneity in effect of LDK addition depending on prior morphine use, we will compare treatment effect between the two groups (no prior morphine use vs prior morphine use). If we assume the two groups to have equal size (78 patients) then the expected SE of the difference between treatment effects of the two groups (no prior morphine vs prior) will be 0.64, i.e. the corresponding 95% confidence interval will have a width of approximately 2.6.

To handle potential differences in baseline pain intensity between the standard and the LDK treatment group, we will assess the relative (%) change in NRS from baseline (T0) to 10 min after administration of study medicine in a supplemental post-hoc analysis. The relative change in pain scores will be assessed by multilevel mixed effect ordinal logistic regression model.

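### The SAP calls the study an equivalence trial, but the protocol designs and sizes it for superiority, and the stated decision rule cannot show equivalence

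*SAP*

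**What the plan says.** The SAP, dated 15 September 2023 and stated to precede receipt of the A and B lists, sets the framework in its second paragraph: "This study will be undertaken as an equivalence trial with the application of intention to treat analysis". It then plans a comparison of the 10-minute NRS change by a test chosen on distribution, Mann–Whitney tests of NRS at the various times, and a model for the normal case: "If normal distributed a multilevel mixed effects linear regression will be carried out". Its decision rule is "All P-values will be two-sided, and those below 0.05 considered significant". It describes these analyses as brief and refers to a fuller signed plan in the Trial Master File.

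The protocol points the other way in four places:

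- Section 2.1.1: "This is an investigator-initiated, randomized, parallel-grouped, double-blinded, superiority trial".
- Section 2.1.2, first hypothesis: "The combination of IV LDK and IV morphine will be superior to IV morphine alone as regards analgesic effect".
- Section 4.1.2: "This study is powered to detect a difference in pain reduction of at least 1.5 on the NRS scale between the groups".
- Section 5.1: a mean reduction of 1 point is expected in the control group, and 2.5 is required "in the intervention group for the addition of LDK to be meaningful".

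The protocol's amendment log, which ends at version 3.2 in May 2023, records no change of objective.

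**The concern.** Superiority and equivalence trials ask opposite questions. An equivalence claim needs a margin fixed in advance and an interval shown to lie inside it. The supplied SAP text names equivalence but provides only tests of difference. In those tests p<0.05 rejects *no difference*, and p≥0.05 establishes nothing about closeness. The stated framework therefore cannot be answered by the stated rule.

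What is at stake is the wording of a null result. The SAP is the later document and the one that governs analysis. Its opening sentence leaves room to describe a non-significant comparison as equivalence, although no criterion for equivalence appears in the supplied text. This applies to the pooled primary comparison and to the two opioid-use sub-analyses that the SAP places under the primary outcome.

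**Working it through.** **1. Which framework does the sample size belong to?** Inputs from protocol section 5.1: difference 2.5 − 1 = 1.5, SD 2 in each arm, alpha 5%, power 90%, two-sample t-test. Section 5.2 makes all tests two-sided.

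- Normal approximation: n = 2 × [2 × (1.960 + 1.282) / 1.5]² = 37.4, so 38 per arm.
- Exact t-test solution: 38.35, so 39 per arm. This matches the protocol.
- Check at 39 per arm: standard error 2 × √(2/39) = 0.453; noncentrality 1.5 / 0.453 = 3.31 on 76 df; power 90.5%. At 38 per arm power is 89.7%.
- A one-sided 5% version (normal approximation) gives 31 and does not match.

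The stated size is a two-sided superiority calculation.

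**2. Is there a margin?** None appears in the supplied text. The only candidate figure, 1.5 points, is described in sections 4.1.2 and 5.1 as a benefit to be detected, not a limit within which arms count as alike.

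**3. How often would there be a null result to misread?** Inputs: n = 116 from the SAP; SD 2 from section 5.1. Assumptions: equal arms (116 / 2 = 58) and, for the sub-analyses, an equal split by opioid use (58 / 2 = 29 per arm). The SAP does not give that split. Two-sided t-test at 0.05, noncentral t; standard error = 2 × √(2/n); 95% half-width = t(0.975, 2n − 2) × standard error.

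| Per arm | Standard error | 95% half-width | Non-significant at true 1.0 | Non-significant at true 1.5 |
|---|---|---|---|---|
| 58 (pooled) | 0.371 | 0.74 | 23.9% | 2.0% |
| 29 (each sub-analysis) | 0.525 | 1.05 | 53.5% | 19.9% |

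The pooled 2.0% at 1.5 points becomes 0.04% if the SD is 1.5 and 10.7% if it is 2.5. A simulated Mann–Whitney test on normal changes rounded to whole numbers (4,000 runs) gives similar values: 27.7% and 3.0% at 58 per arm, 56.7% and 22.4% at 29.

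These are type II error rates and are identical under either label. They count opportunities for misreading, not errors caused by the word.

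**4. Could a non-significant result still be compatible with the protocol's meaningful benefit?** At a true difference of 1.0, a non-significant result whose 95% interval includes 1.5 occurs 2.2% of the time pooled and 38.3% of the time at 29 per arm (400,000 simulated draws). The ambiguity lies mainly in the sub-analyses.

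**The case against.** The strongest reply is that little follows from one word. Tests, threshold and data are the same whether or not it is corrected. The SAP never says that p≥0.05 will be called equivalence. Protocol section 5.2 commits to CONSORT reporting and 95% intervals, section 6.5 has alternative conclusions drafted while the groups are still coded A and B, and section 12 allows for an inconclusive finding. At the protocol's own 1.5 points the pooled analysis yields a null result only 2% of the time; the 24% figure uses a true difference of 1.0, which is not the design target. Most of this stands and limits the severity. It does not remove the conflict, because none of these sections says how a null result is to be worded.

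Four stronger readings are tempting and are not supported:

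- *That no margin exists.* The fuller plan in the Trial Master File was not supplied. A margin there would leave the conflict with the protocol standing, as an unrecorded change of objective.
- *That the team intends to claim equivalence from non-significance.* The SAP does not say so.
- *That 1.5 points is a hidden margin.* Two one-sided 5% tests with margin 1.5, true difference zero and 90% power need 2 × [2 × (1.645 + 1.645) / 1.5]² = 38.5, also 39 per arm. This is coincidence: 1.645 + 1.645 = 3.29 happens to lie close to 1.960 + 1.282 = 3.24.
- *That the label spoils the side-effect hypothesis.* The protocol expects that "The frequency of side effects will be similar in the two treatment groups". Testing similarity with a test of difference is a separate question and would arise equally under a superiority label.

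**Conclusion.** The conflict is plain on the text and should be fixed. The SAP's stated framework contradicts protocol sections 2.1.1, 2.1.2, 4.1.2 and 5.1, and the only decision rule in the supplied text cannot deliver an equivalence conclusion. Confidence is high for the contradiction. It does not extend to saying that no margin was ever set.

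The demonstrated consequence is limited to the naming of a non-significant result. That exposure is small in the pooled analysis at the design difference and larger for smaller true effects and in the sub-analyses, where it rests on the assumed SD of 2, equal arms and 29 per arm.

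**What to change.** Issue a dated correction to the SAP that says whether the A and B lists had been obtained when it was made. It should:

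1. Replace the equivalence label with superiority, in line with protocol sections 2.1.1 and 2.1.2.
2. Keep the planned tests and the p<0.05 threshold.
3. State that a non-significant primary result, pooled or in either opioid-use sub-analysis, is reported as *superiority not shown*, with the estimated difference and its 95% confidence interval, and not as equivalence. Name the interval that accompanies a Mann–Whitney test. On whole-number scores its limit can fall exactly at zero beside a significant p-value, so the test remains the decision rule.

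If equivalence was intended, record it instead as a dated change of objective and publish the margin and the interval rule, with evidence that both were fixed before the A and B lists were obtained.

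For the superiority correction the cost is a few sentences, with no new data and no change to any planned test.

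### Primary 10-minute NRS test: the public plan gives no rule for choosing it and no adjustment for T0 NRS or prior opioid use; one prespecified ANCOVA would supply both

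*SAP*

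**What the plan says.** The SAP's primary outcome paragraph compares "average change of NRS at 10 minutes between the intervention and control group and analyzed using appropriate test depending on distribution". For NRS at the successive time points it names the Mann–Whitney U test and adds: "If normal distributed a multilevel mixed effects linear regression will be carried out". It lists no model terms and does not say how T0 enters. T0 NRS comes up in the SAP only for comparing patients with and without prior opioid use: "Appropriate test according to potential difference in NRS at T0 in the two groups (prior opioid use) will be applied".

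Protocol section 5.1 compares continuous outcomes "using t-tests or Wilcoxon rank-sum test as appropriate". "To handle potential differences in baseline pain intensity between the standard and the LDK treatment group", it plans a supplemental, post-hoc analysis of percentage change: "The relative change in pain scores will be assessed by multilevel mixed effect ordinal logistic regression model".

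The protocol schedules NRS at T0 (section 2.5.1) and gives each opioid group its own series of randomisation numbers (section 2.2). The SAP describes itself as brief and refers to a detailed plan in the Trial Master File, which is not public.

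**The concern.** The public text makes the primary test depend on the distribution but gives no criterion for deciding. Candidate tests are named; the rule that picks one is not. The choice also changes the estimand. The outcome is an average change, and protocol section 4.1.2 states "This study is powered to detect a difference in pain reduction of at least 1.5 on the NRS scale between the groups", so a mean difference appears to be the target. If the rank test is used, the test no longer addresses that mean difference and brings no confidence interval for it.

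No stated primary test is said to adjust for T0 NRS or opioid stratum. Adjustment gains precision when 10-minute NRS follows T0 NRS with a slope below 1, or when the opioid groups differ in mean reduction. Protocol section 2.1.2 expects that ketamine with morphine "will provide a larger reduction on the NRS scale for patients with a prior use of opioids"; that alone would make the groups differ. Precision matters most for the within-group results and for the comparison of effects between opioid groups.

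**Working it through.** **Inputs from the documents.** SD of change 2 in each arm, difference 1.5 points, alpha 5%, power 90% (protocol 5.1); two-sided testing and n = 116 (SAP); 1:1 allocation in blocks of 2, 4 and 6, with separate number series by opioid group (2.2); entry at NRS 5 or more (2.1.4).

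**Assumed, not in the documents.** 58 per arm, with 29 per arm in each opioid group; blocking within each series; slope *b* of 10-minute NRS on T0 NRS; SD *s* of T0 NRS; difference *d* in mean reduction between opioid groups.

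**1. The plan's own figures.** Normal approximation: 2 × 2² × (1.960 + 1.282)² / 1.5² = 37.4, so 38 per arm. The exact t-test gives 38.35, so 39 per arm (power 90.5%), as stated. The stated SE for the difference in effects also reproduces: √(4 × 2² / 39) = 0.64.

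**2. Unadjusted analysis at n = 116.** SE = 2√(2/58) = 0.371 and half-width 1.96 × 0.371 = 0.73. Power is 98.0% for 1.5 points and 76.1% for 1.0 point. Within one opioid group, power for 1.5 points is 80.1%. The SE of the difference in effects is √(4 × 4 / 29) = 0.74, against the planned 0.64.

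**3. T0 adjustment, closed form.** Residual variance ratio = 1 − (1 − b)² s² / 4.
- b = 0.7, s = 1.0: 1 − 0.09 × 1 / 4 = 0.978.
- b = 0.3, s = 1.71 (the SD of an even spread over 5–10): 1 − 0.49 × 2.92 / 4 = 0.642.
- b = 1: ratio 1, no gain.

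Over this range the variance falls by 2% to 36%.

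**4. T0 and stratum adjustment, simulation.** 4,000 trials per cell, integer NRS, T0 confined to 5–10 (realised SD 1.41), HC3 standard errors, d = 0. The true effect is 1.0 point except in the last column. Entries are unadjusted → ANCOVA.

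| Slope | SE | 95% CI half-width | Power at 1.0, % | SE of difference in effects | Within-group power at 1.5, % |
|---|---|---|---|---|---|
| 0.3 | 0.366 → 0.324 | 0.73 → 0.64 | 76 → 86 | 0.733 → 0.650 | 80.7 → 88.9 |
| 0.5 | 0.365 → 0.348 | 0.72 → 0.69 | 75 → 80 | 0.730 → 0.698 | 79.2 → 82.7 |
| 0.7 | 0.363 → 0.361 | 0.72 → 0.72 | 75 → 76 | 0.727 → 0.726 | 78.9 → 79.8 |
| 1.0 | 0.356 → 0.364 | 0.71 → 0.72 | 74 → 73 | 0.713 → 0.731 | 78.4 → 75.8 |

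At slope 0.3 the variance ratio is (0.324 / 0.366)² = 0.78, a 22% reduction. At slope 1.0 the SE is 0.364 / 0.356 = 1.02 times as large. HC3 ANCOVA rejected 4.5–4.7% under the null. With ordinary model SEs (a separate 3,000-trial run) the ANCOVA SEs are 0.318, 0.342, 0.354 and 0.358, so the loss at slope 1.0 is under 1%.

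**5. Stratum alone.** The variance falls by (d²/4) / (4 + d²/4): 0.25 / 4.25 = 5.9% at d = 1.0, and 0.5625 / 4.5625 = 12.3% at d = 1.5. Stratified allocation balances this difference but the unadjusted t-test counts it as noise, so its type I error drops to about 4.3% and 3.6%. Simulated power at 1.0 point, t-test against stratum only, is 72–74% against 74–76% (d = 1.0) and 69–72% against 74–76% (d = 1.5). At d = 0 there is no gain.

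**6. The open test choice.** In null simulations, an assumed Shapiro–Wilk rule choosing between t-test and Mann–Whitney rejected 4.5–5.4%. Taking the smaller of the two p-values rejected 5.3–6.4%. Both arms passed the normality check in only 11–30% of those null trials, because NRS is a bounded integer scale. Such a rule would usually lead to the rank test.

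**7. The mixed model.** With T0 as a repeated outcome, an arm-by-time term and a random intercept, the 10-minute estimate equals the unadjusted change difference, whether two or all seven time points are used (complete data). The SE also matches with two time points. With seven it differs, because the model pools variance across times. With T0 as a covariate the model is an ANCOVA. The SAP sentence fits either.

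**The case against.** The detailed plan may already hold the criterion and the model terms, so the public text shows only incomplete wording. That stands, and it limits the finding.

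Nothing is lost at the trial's own effect size: overall power for 1.5 points is about 98% unadjusted, and type I error is sound. That also stands. The larger power gains are at 1.0 point, which the documents do not name as a target, and at the most favourable slope shown.

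The gain rests on a slope and a T0 SD that the documents do not give, and the NRS 5 entry limit narrows the spread of T0. This is correct, and it is why a range is shown. At slope 1.0, HC3 adjustment costs about 2 to 3 percentage points of within-group power (78.4% to 75.8%).

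Replacing the primary analysis after unblinding would itself be post hoc. The SAP predates receipt of the A and B lists, but the documents do not show what has happened since. The fix therefore needs that condition.

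The SAP calls the trial an equivalence trial and protocol section 2.1.1 calls it a superiority trial. ANCOVA does not resolve that, but an adjusted mean difference with its interval serves either reading.

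**Conclusion.** The concern holds for the public text, as a point to consider. The primary arm comparison has no stated selection criterion and no named covariates, and the plan leaves baseline difference between arms to a post-hoc percentage-change analysis. A t-test on change remains valid.

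For T0 SDs of 1.0 to 1.71 and slopes of 0.3 to 0.7, T0 adjustment lowers the residual variance by 2% to 36%. In the integer-scale simulation with HC3, the variance of the effect estimate falls by 22%, 9% and 1% at slopes 0.3, 0.5 and 0.7, with a small loss at slope 1.0. Stratum adjustment adds a few points of power only if the opioid groups differ in mean reduction. All of this assumes a change SD of 2 and an even split of 116. The more dependable benefit is one analysis fixed in advance that estimates the quantity the trial was sized on.

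**What to change.** Name one primary analysis, whatever the distribution: linear regression of 10-minute NRS (or change) on treatment, T0 NRS and prior-opioid stratum, reporting the adjusted mean difference with its 95% CI. State which standard error is used; HC3 held its level in the simulations.

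- For the opioid-group comparison, use the same model with a treatment-by-stratum term in place of a test chosen on the T0 difference.
- If the mixed model is kept, state that T0 enters as a covariate, or with a common T0 mean across arms.
- Keep a stratified rank test as a named sensitivity analysis, and percentage change as supplemental only.
- If the Trial Master File plan already settles this, copy its wording into the public SAP.
- If the allocation is already known, label the ANCOVA as an added analysis and do not present it as the prespecified primary.

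The cost is SAP wording, since both covariates are already collected. At worst (slope 1, no stratum difference) the HC3 SE is about 2% larger overall and about 4% larger within an opioid group; with ordinary SEs the loss is about 1% or less.

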#### 3.2 Inclusion criteria

PI will screen ED patients at ED admission for the following inclusion criteria:

- 1. Emergency Department admission
- 2. Age  $\geq$  18 years and
- 3. A painful condition (NRS  $\geq$  5)
- 4. Stable vital signs defined as systolic blood pressure ≥ 90 mmHg, heart rate between 50 and 150 per minute, respiratory rate between 8 and 30 per minute, oxygen saturation greater than or equal to 92%.

Further subcategorized into

1. Prior use of opioids (daily for one week before admission)

2. No prior use of opioids (daily for one week before admission)

These broad inclusion criteria are chosen to investigate the effect of LDK in the entire, broad population with pain in the ED and the subcategorization to investigate whether LDK leads to a larger reduction on NRS in the group of patients with a prior use of opioids than those without a prior use of opioids.

We will strive to enroll participants as soon as they fulfill the criteria in the ED.

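### The SAP analyses 116 patients where protocol 5.1 needs 156, so the per-group 90% power and the SE of 0.64 cannot both be met, and its between-group comparison is ambiguous

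*SAP*

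**What the plan says.** **Size.** Protocol 5.1 assumes a mean reduction of 1 point on control and 2.5 on LDK, SD 2 in each arm, alpha 5%, power 90% and a two-sample t-test. It concludes that "a sample size of 78 patients is required; 39 in each treatment arm (two independent samples =156 patients"). Section 2.3.1 accordingly sets four cells of 40, and the Overview and section 2.1.4 give a target of 160. Section 5.1 then states a precision for the contrast between the opioid-use groups: "If we assume the two groups to have equal size (78 patients) then the expected SE of the difference between treatment effects" is 0.64, with a 95% confidence interval about 2.6 wide.

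The SAP, dated September 2023, states that "Primary outcome includes initial analysis of all included patients (n=116) and sub-analysis in two groups (prior opioid use / no prior opioid use"). It does not mention 156 or 160 and states no power or SE of its own.

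**Contrast.** Protocol 5.1 says "we will compare treatment effect between the two groups (no prior morphine use vs prior morphine use"). Section 3.2 gives the purpose of the subcategories as finding out "whether LDK leads to a larger reduction on NRS in the group of patients with a prior use of opioids than those without". The second hypothesis in 2.1.2 is looser: the combination "will provide a larger reduction on the NRS scale for patients with a prior use of opioids than for patients" with none. The SAP promises an unnamed test, chosen according to a possible difference in NRS at T0, which "in the two groups (prior opioid use) will be applied for comparing the differences in NRS between the two groups".

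The SAP presents itself as a brief version and closes with "Detailed statistical plan are written, printed, signed and stored in Trial Master File". That detailed plan is not among the documents.

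**The concern.** The only planning figures on record rest on 78 patients per opioid-use group. Two groups of 78 need 156 patients, and the SAP has 116. A non-significant result in one group, or for the contrast between groups, would be read against 90% power and an SE of 0.64 that the trial no longer has.

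The between-group sentence adds a second difficulty. It mentions neither LDK, placebo, treatment effect nor interaction, and it labels the two groups by prior opioid use. An analyst could follow it and compare pain reduction between prior users and others over both arms. That comparison mixes the question about LDK with any difference in how the two populations respond to morphine alone. The documents give no reason to take that difference as zero: section 2.3.1 defines the morphine dose differently in the two groups, and section 1.1.1 describes opioid-tolerant patients as needing much larger opioid doses for relief. Its sign is unknown.

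**Working it through.** **Inputs.** Difference 2.5 − 1 = 1.5, SD 2, two-sided alpha 0.05 (protocol 5.1 and 5.2); 1:1 allocation (2.2); N = 116 (SAP). *Assumptions:* arms balanced within each opioid-use group, every patient has a 10-minute NRS, no baseline adjustment. The split of 116 is not given, so a range is shown.

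**Step 1: reproduce the protocol.** Power of a two-sample t-test with n per arm uses the noncentral t with 2n − 2 degrees of freedom and noncentrality 1.5 / (2·√(2/n)).
- n = 38 gives 89.7% and n = 39 gives 90.5%, so 39 per arm is the smallest size reaching 90%, as stated.
- The LDK effect in a group of a patients (a/2 per arm) has variance 4/(a/2) + 4/(a/2) = 16/a. The difference between two groups' effects therefore has SE = √(16/a + 16/b).
- At 78/78, SE = √(0.2051 + 0.2051) = 0.6405, which matches 0.64. The interval width is 3.92 × 0.6405 = 2.51, or 2.56 with a multiplier of 4; the stated 2.6 is a matter of rounding.

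**Step 2: put in 116.**

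| Split of patients | Power, larger group | Power, smaller group | SE of difference in effects | 95% CI width (3.92 × SE) |
|---|---|---|---|---|
| 78/78 (plan) | 90.5% | 90.5% | 0.641 | 2.51 |
| 58/58 | 80.1% | 80.1% | 0.743 | 2.91 |
| 70/46 | 87.1% | 70.1% | 0.759 | 2.98 |
| 78/38 | 90.5% | 61.4% | 0.791 | 3.10 |
| 90/26 | 94.0% | 45.1% | 0.891 | 3.49 |

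The smaller group cannot exceed 58, so its power cannot exceed 80.1%. The sum 16/a + 16/(116 − a) is smallest at a = 58, so the SE cannot fall below 0.743, which is 0.743/0.6405 = 1.16 times the planned value. The smallest difference in LDK effect detectable with 80% power (noncentral t, N − 4 degrees of freedom) rises from 1.81 points at 78/78 to 2.10 at 58/58, and further at uneven splits.

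**Step 3: pooled comparison.** With 58 per arm, power for 1.5 points is 98.0%.

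**Step 4: what the between-group sentence could estimate.** Among patients with no prior use, let mean reduction be m on placebo and m + L on LDK. Among prior users, let it be m + d on placebo and m + d + L + I on LDK. Here d is the difference in response to morphine plus placebo, and I is the difference in LDK effect. Three readings fit the SAP sentence:
1. LDK versus placebo, within or allowing for opioid-use group. This estimates L, L + I or a mixture, and does not compare the groups.
2. A contrast of the two LDK effects: (L + I) − L = I. This is what protocol 5.1 and 3.2 plan.
3. Prior versus no-prior users over both arms: [(m + d) + (m + d + L + I)]/2 − [m + (m + L)]/2 = d + I/2.

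On the third reading, a true I of 1.5 is cancelled by d = −0.75, and with I = 0 the result is d alone. These values only illustrate the algebra; the documents give neither d nor I.

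The second hypothesis in 2.1.2, taken word for word, compares the two LDK cells, (m + d + L + I) − (m + L) = d + I. So the support for I comes from 5.1 and 3.2, and not from the hypothesis as worded.

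**The case against.** The strongest reply is that nothing here is contradicted. The 0.64 is explicitly conditional on 78 per group. Ninety per cent per group is inferred from the doubling to 156 and the four cells of 40, and is not stated in those words. The protocol claims no power for the contrast between groups, only a precision. The SAP is a summary, and the Trial Master File may hold the split, the reason for 116 and the model. The CONSORT diagram will show the counts. Nor does the SAP withdraw the protocol's commitment to compare treatment effects, and its paragraph opens with intervention versus control, so a benign reading of the later sentence is available.

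Much of this is fair. It limits the point to the published SAP and makes its second part a request for clarification. It does not remove the point. The condition behind 0.64 cannot be met with 116 patients, no other figure has been published, and a flow diagram neither restates precision nor defines a contrast.

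A reader might go further, and the documents do not support it:
- *That the primary comparison is underpowered.* The pooled superiority test keeps about 98%.
- *That each group has at most 80%.* This is true only of the smaller group; a group of 78 still has 90.5%.
- *That the SAP will run the wrong analysis.* The d + I/2 result arises on one of three readings.

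**Conclusion.** The point holds in this limited form and should be fixed. With 116 patients, under the protocol's SD of 2, difference of 1.5 and superiority test, 90% power cannot hold in both opioid-use groups. The smaller group has at most 80.1%, and 61.4% if the other kept its planned 78. The SE of the difference in treatment effects is at least 0.743 against 0.64, and the interval at least 2.9 wide against the stated 2.6 or so. Missing 10-minute scores would make these figures worse; adjustment for T0 could improve them. The arithmetic is certain given these inputs and balanced arms.

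The between-group sentence is ambiguous and not shown to be wrong. What is at stake is how the group results and the contrast are interpreted; the pooled superiority result is not affected. The SAP also calls the trial an equivalence trial and gives no margin, whereas protocol 2.1.1 says superiority. That is a separate issue, and the power figures here do not apply to an equivalence test.

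**What to change.** 1. Confirm that 116 is the number included, explain it, reconcile it with 160, and give counts by opioid-use group and arm. State that the 90% per-group power and the SE of 0.64 no longer apply. Replace them with figures for the actual group sizes a and b: SE = √(16/a + 16/b), which is at least 0.743, and power for each group separately, at most about 80% in the smaller one.

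2. Replace the between-group sentence with: *The comparison of treatment effect between opioid-use groups (protocol 5.1 and 3.2) is the treatment-by-prior-opioid-use interaction in a linear model of change in NRS at 10 min with treatment, prior opioid use, their interaction and NRS at T0, reported with its 95% CI. Within-group effects are reported as estimates with 95% CI, and significance in one group but not the other is not taken as evidence of a difference.*

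Including T0 also deals with the SAP's own worry about a T0 difference. It may recover precision: 0.743·√(1 − r²) is 0.709 at r = 0.3 and 0.643 at r = 0.5, where r is the correlation of T0 NRS with change (assumed; not in the documents).

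If the plan in the Trial Master File already says this, quote it. Date the change relative to receipt of the A and B lists.

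**Cost:** a few sentences, one extra model and less favourable stated figures. T0 NRS and prior opioid use are already collected, so no patients or data are added.
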